## 8.2 Adverse Events

Adverse events will be recorded using standardized forms and reported to the study clinician at each site; in addition, quarterly reports will be provided to the study DSMB and more as needed in the event of unexpected adverse events, such as events that are not known and commonly documented side effects of PrEP. Although no serious adverse events are anticipated, these will be reported to the IRB, the study DSMB, and NIH within 24 hours of the MPI becoming aware of them. Following NIH guidelines, adverse events will be defined as “any untoward or unfavorable medical occurrence in a human study participant.” *Serious adverse events* will be adverse events that result in death, are life threatening, requires or prolongs hospitalization, causes disability, or poses other significant hazards. Severity of AEs will be classified as follows: mild, moderate, and severe. Mild AEs will be events that do not require medical attention and are easily tolerated. Moderate AEs will be events that require simple and routine medical treatment and may cause some interruption to daily life. SAEs will be defined as above. AEs will also be categorized as definitely, possibly, or not related to the study. AEs that are definitely related will follow a logical causal sequence from a study activity. Possibly related events will follow a logical causal sequence from a study activity but may also be due to non-study activities. Not related events will be events that do not follow a logical causal sequence from any study activity.

## 9. STATISTICAL CONSIDERATIONS

### 9.1 Primary Outcome

Assessment of TFV-DP will be conducted at 6 and 12-month follow-ups. Differences in the proportion of participants with protective levels of TFV-DP between the intervention arm and the control arm will be tested using two-proportion z-tests with pooled variances, based on intent-to-treat assignment. The percentage of participants with protective levels of TFV-DP at months 6 and 12 will be compared using a Generalized Linear Mixed Model (GLMM) logistic regression model that accounts for within-participant correlation over time, of the form:  $\text{logit } \pi_{ij} = \beta_0 + \beta_1$

$\beta_2 \text{rm}_{ij} + \beta_3 (\text{time}_{ij}) + \beta_4 (\text{rm}_{ij} \times \text{time}_{ij})$ , where  $\pi_{ij}$  represents the outcome at time  $j$  on participant  $i$ ,  $\beta_0$  represents a random intercept for participant  $i$ , and fixed effect dummy variables are included for intervention arm, time, and the interaction between arm and time. The statistical model will be used to estimate the proportion of participants with protective levels of TFV-DP (plus 95% confidence intervals) by intervention assignment and time on study. The statistical test for interaction between arm and time will be the primary overall test to determine whether PrEP protection changed in significantly different ways during follow-up (at  $\alpha = 0.05$ ). If a significant time\*intervention interaction is detected, we will test differences between the model-based adherence estimates at each time point. If protective levels of PrEP rates are consistently different or similar (i.e., no interaction) then the main effect test for intervention assignment will be used to evaluate intervention efficacy.

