### 3. STUDY OVERVIEW

#### 3.1 Study Design

The study is a stratified randomized, controlled trial comparing PrEP@Home intervention care to standard of care control (i.e. patients being seen quarterly in clinic with a provider), with primary outcome of having protective levels of TFV-DP (700 fmol/ml or greater) and secondary outcome of retention in PrEP care, as measured by photo of dated prescription label.

[figure not shown]
A screening will be conducted online and involve a screening consent and questions to determine initial eligibility. This will be followed by a full consent (if eligible), a baseline survey, and the return of self-collected specimens for testing to determine clinical PrEP eligibility. Those eligible for the study will be enrolled into the trial and randomized to either intervention (PrEP@Home) or control (standard of care). Participants assigned to the PrEP@Home intervention will have a baseline teleconsultation with a site study clinician who will be responsible for prescribing PrEP as indicated. Intervention participants enrolled prior to May 2022 will be offered telemedicine consultations at 1, 3, 6, 9 and 12 months, and will complete quarterly home specimen collection for laboratory tests recommended by CDC at each time period. Individuals enrolled after May 2022 will be offered telemedicine consultations at 1, 3, and 6 months, and will complete quarterly home specimen collection for laboratory tests recommended by CDC at each time period. The study virtual visits consist of surveys, specimen collection, and telemedicine consultation. Those assigned to the control condition will be referred to a publicly available website that geolocates the nearest PrEP provider, [www.PrEPLocator.org](http://www.PrEPLocator.org). Both conditions will have identical TFV-DP kit collection for primary outcome assessments at month 6 (and 12 months for those enrolled before May 2022) and app-based surveys for secondary outcomes assessments at baseline, 3, 6, (and 9 and 12 months for those enrolled before May 2022).

Study sites in Atlanta, GA, Boston, MA, Jackson, MS, St. Louis, MO, and Cleveland, OH, will allow for recruitment to focus on MSM known to be at highest risk of acquisition and with documented lower levels of persistence in PrEP care. The sample of 396 will be composed of at least 50% Black and 50% younger (aged 18-34) participants, including at least 25% YBMSM.

[figure not shown]

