## 5. TRIAL DESIGN

### 5.1 Study Arms

The Intervention group will be assigned to using the PrEP@Home system for 6 months and/or one year of follow-up PrEP care, including telemedicine visits if needed and home test kits. Participants in the Intervention group will have full access to the application. All PrEP consultations will be conducted via telemedicine unless there is a clinical need to be seen in-clinic. Participants will have the option of coming to the clinic for in-person linkage to care at the end of study, if clinics are open.

The Control group will be actively linked to a local PrEP provider for standard of care follow-up. Participants in the Control group will see portions of the study app pertinent to their participation in the study, including electronic surveys and kit tracking for the mail DBS card for TFV-DP. Partner institutions at each site are already implementing PrEP as standard of care in their community, and participants will be referred to these institutions for PrEP care. Each study site will have designated local clinics that have agreed to provide standard PrEP care to control arm patients.

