### 5.2 Randomization

Upon completion of stage 3 eligibility assessment (successful initiation of PrEP as determined by photo of prescription label), participants will be randomized to either intervention (PrEP@Home, n=264) or control (standard of care, n=132). Participants will be randomized using an electronic data system, DFExplore. We will implement a stratified randomization scheme using categories of age (18-34, 35-49) and study site to decreases the likelihood of Type I error due to the expected association between covariates and study outcome. An uneven allocation ratio of 2:1 (Intervention : Control) will facilitate subgroup analyses and modeling for Aims 2 and 3 by allowing for larger intervention group size.

All randomization will be accomplished within the study data management platform; within each stratum, the data system will produce a sequential block randomization list. This list, not viewable by study PI's or the study statistician, will automatically populate the appropriate study arm assignment in the electronic data system at the time each new participant is randomized at any of the four study sites.

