### 9.2 Power to detect effects in primary outcomes

A total of 396 participants will be enrolled at baseline to account for a 10% expected loss to followup during 12-months of study follow-up. With this sample size and assuming  $\alpha=0.05$  and two-sided significance, there will be 80% power to detect absolute differences between the intervention and control arms in the proportion of subjects with protective levels of TFV-DP of > 15.8% when the average proportion in the control group is 0.50. Power calculations were performed using PASS v.13 software (NCSS, LLC. Kaysville, Utah). Hypothesis is participants randomized to PrEP@Home will have higher levels of protection against HIV infection as

determined by levels of emtricitabine triphosphate (TFV-DP) than standard of care controls.

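### With month-12 cards from one enrolment period only, the section 9.1 mixed model can read an arm effect that differs between periods as one that changes over time

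*Combined protocol and SAP*

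**What the plan says.** Section 3.1 sets TFV-DP collection for "primary outcome assessments at month 6 (and 12 months for those enrolled before May 2022"; section 6.3 confirms that later enrollees give a month-6 card only. Section 9.1 specifies a logistic mixed model with a participant random intercept, in which "fixed effect dummy variables are included for intervention arm, time, and the interaction between arm and time". The arm-by-time test at 0.05 is the primary overall test. If it is significant, the arms are compared at each time point; if not, the main effect of arm is used to judge efficacy.

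Enrolment period appears nowhere in this analysis. It is not a randomization stratum (section 5.2 uses age and site), not a named covariate in section 9.2.1, and not a named subgroup in section 9.3. Nothing limits the arm-by-time test to men scheduled for both cards. Section 9.1 also plans two-proportion z-tests, which do not use the mixed model.

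**The concern.** Month 6 averages over two cohorts and month 12 samples one of them. A contrast between the two visits therefore mixes change within men with any difference in arm effect between cohorts. The random intercept removes part of this, because men with both cards inform the model about themselves, but not all of it.

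Two things are at stake. First, a significant interaction would send the analysis to per-visit tests, and be reported as an effect that grows or fades with time on PrEP, when the cause is who was enrolled when. Second, the model-based month-12 difference would describe neither the early cohort nor the whole trial.

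**Working it through.** **Inputs from the documents.** Two-sided alpha 0.05 (section 9.1 and 9.2); "two-sided significance, there will be 80% power to detect absolute differences between the intervention and control arms" of "15.8% when the average proportion in the control group is 0.50"; "A total of 396 participants will be enrolled at baseline"; "10% expected loss to followup during 12-months of study follow-up"; "An uneven allocation ratio of 2:1 (Intervention : Control". After 10% loss, 396 × 0.9 = 356 men are analysed: 118.8 control and 237.6 intervention.

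**Assumed, because the documents do not say.** The share enrolled before May 2022 (one quarter, half, three quarters); the arm effect in each period; and the random-intercept SD. An SD of 1.5 gives a latent intraclass correlation of 1.5²/(1.5² + π²/3) = 0.41; an SD of 3.0 gives 0.73.

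**Step 1: the plan's own figure.** For 0.50 v 0.658, the pooled proportion is (0.50 + 2 × 0.658)/3 = 0.605. The null SE is √[0.605 × 0.395 × (1/118.8 + 1/237.6)] = 0.0549. The alternative SE is √[0.25/118.8 + 0.225/237.6] = 0.0552. Power = Φ[(0.158 − 1.96 × 0.0549)/0.0552] = Φ(0.91) = 81.9%, which agrees with the stated 80% to within 2 points.

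**Step 2: the spurious interaction.** Let the arm effect be constant over time within each period. Control is 0.50 at both visits, so its logit is 0. With early share s, the intervention proportion is s × p(early) + (1 − s) × p(late) at month 6 and p(early) at month 12. The arm-by-time coefficient is then

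β = logit[p(early)] − logit[s × p(early) + (1 − s) × p(late)],

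where the true change over time is zero. Fitting the planned mixed model to exact outcome probabilities returns the same β. Its rejection rate is Φ(−1.96 + β/SE) + Φ(−1.96 − β/SE), with the SE for 356 men at correlation 0.41.

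| Effect early v late (points) | Share early | Month-6 intervention proportion | β | SE | Rejection |
|---|---|---|---|---|---|
| 15.8 v 0 | 1/4 | 0.5395 | 0.50 | 0.66 | 12% |
| 15.8 v 0 | 1/2 | 0.579 | 0.34 | 0.49 | 10.5% |
| 15.8 v 0 | 3/4 | 0.6185 | 0.17 | 0.42 | 7% |
| 25 v 5 | 1/4 | 0.60 | 0.69 | 0.67 | 18% |
| 25 v 5 | 1/2 | 0.65 | 0.48 | 0.50 | 16% |
| 25 v 5 | 3/4 | 0.70 | 0.25 | 0.43 | 9% |

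For 25 v 5, simulation (600 trials each, likelihood-ratio test) gave 19.2% with one quarter early and 15.8% with half. At correlation 0.73 the rates are lower: about 6% to 9% for 15.8 v 0, and 7.5% to 12% for 25 v 5. With the effects reversed (0 early, 15.8 late) the coefficient turns negative, −0.48 to −0.16.

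**Step 3: the month-12 estimate.** For 25 v 5 with half early and correlation 0.41, the model's fitted differences are 15.0 points at month 6 and 22.4 at month 12. The month-6 figure is the whole-trial average, (25 + 5)/2 = 15. The month-12 figure is neither the early cohort's 25 nor the trial's 15.

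**Step 4: level difference only.** With 0.50 v 0.658 early and 0.40 v 0.564 late (nearly the same odds ratio), β is at most 0.015 and rejection stays at 5%.

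**Step 5: candidate repairs.**
- Period main effect alone: for 25 v 5, half early, β is still 0.46 and rejection 15%.
- Period plus period by arm: β = 0.00 and rejection 5% (simulation 4.3% and 5.5%).
- Test confined to the early cohort: about 4% in simulation.
- Coding matters. Under a constant effect (0.50 v 0.658 in both periods, half early, SD 1.5), uncentred period-by-arm dummies with late enrollees as reference turn the arm coefficient into a late-period effect. In two small simulations, power of the main-effect test went from 93% under the planned model to 59%, and from 90% to 54%. Centring period restored 93.5% and 90%.

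**The case against.** The strongest reply is that the differing arm effect is supposed, not documented. The remark in section 5.1 about "in-person linkage to care at the end of study, if clinics are open" concerns optional linkage for the intervention arm and is not tied to a period. The COVID-19 survey goes to all participants (section 6), and section 3.5.2 allows clinic or Zoom visits without a date limit. This stands. The text makes a period-specific effect plausible, since the comparison is remote against clinic care and the protocol expects clinic access to vary, but it does not show one. The figures are therefore conditional, and effects that vanish in one period are strong scenarios.

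A reader might infer that any difference between periods invalidates the missing month-12 values. Step 4 shows otherwise for this test: only a differing arm effect causes the error.

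A reader might also infer that the plan can manufacture efficacy. It does not do so by this route. Arms are randomized concurrently, so with no arm effect in either period nothing spurious arises. The month-6 estimate remains the whole-trial average, and a month-6 z-test is untouched.

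What survives is narrower: the stated decision rule can take a cohort difference for a time trend, and the month-12 estimate has no clear population.

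**Conclusion.** The point holds conditionally. If the arm effect differs between enrolment periods, the planned arm-by-time test has a false-positive rate above 5%: roughly 7% to 12% when the design difference of 15.8 points is present early and absent late, and 9% to 18% for 25 v 5 points, at correlation 0.41 and across the three enrolment shares. Stronger within-person correlation reduces this, and a larger early share does too. The effects, shares and correlations are all assumptions.

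The consequence is a misdirected decision rule and a mislabelled month-12 estimate. It is not a false claim of efficacy, and the documents do not support saying that the primary comparison as a whole is invalid. Because the interaction is the primary overall test and the repair is nearly free, the plan should be changed.

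**What to change.** Choose one of two practically equivalent routes and state it in section 9.1:

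1. Run the arm-by-time test only in participants scheduled for both cards, and keep all participants in the main-effect model.
2. Add enrolment period and period by arm to the mixed model, with period centred, or with the arm effect standardised over the enrolled period mix, so that the fallback main-effect test still estimates the whole-trial arm effect. A period main effect alone is not enough.

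Under either route, obtain month-12 estimates for the pre-May-2022 cohort and label them so.

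The cost is a few sentences and a variable that follows from the enrolment date. The arm-by-time test becomes less precise: for 15.8 v 0 points at correlation 0.41, its SE rises from 0.66 to 0.77, 0.49 to 0.54 and 0.42 to 0.44 with one quarter, half and three quarters early. Under route 2 the main effect is also somewhat less precise when effects differ by period.

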### 9.2 Power to detect effects in primary outcomes

A total of 396 participants will be enrolled at baseline to account for a 10% expected loss to followup during 12-months of study follow-up. With this sample size and assuming  $\alpha=0.05$  and two-sided significance, there will be 80% power to detect absolute differences between the intervention and control arms in the proportion of subjects with protective levels of TFV-DP of > 15.8% when the average proportion in the control group is 0.50. Power calculations were performed using PASS v.13 software (NCSS, LLC. Kaysville, Utah). Hypothesis is participants randomized to PrEP@Home will have higher levels of protection against HIV infection as

determined by levels of emtricitabine triphosphate (TFV-DP) than standard of care controls.

### **9.2.1 Adjusted analyses**

GLMM models will control for potential confounding for factors such as medication self-efficacy and motivation to take PrEP. (1) Adjusted analyses will be conducted to control for changes in PrEP eligibility over time for participants in each trial arm, per CDC guidelines, using an additional interaction term between eligibility and treatment arm. (2) Per protocol assessments will be conducted that account for potential changes in intervention as delivered; for instance, this would account for participants assigned to the intervention condition opting to instead receive standard of care PrEP from their local clinician.

A number of secondary analyses will be conducted using GLMM models. (3) Intervention impact on the secondary outcome of PrEP prescription persistence will be determined using analogous logistic regression models. (4) Secondary analysis will be conducted to model  $\log_{10}$  (TFV-DP levels), using a linear mixed model. Other specific and aggregate measures of safety include: renal function, HIV incidence, and incident bacterial STI across study arms.

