### **6.3 Follow-up Visits**

Follow-up visits (visits are defined as any interaction with the study data system) will be conducted at Months 1, 3, 6, 9, and 12 for those enrolled prior to May 2022 and 1, 3 and 6 Months for those enrolled after May 2022. The month 1 visit will consist of a brief survey for control participants, and a brief survey and clinical check-in for intervention participants. For intervention participants, home specimen kits for HIV and STI testing will be sent at months 3 and 6 for those enrolled after May 2022 as well as Months 9 and 12 for those enrolled prior to May 2022. Creatinine will be tested at month 3 for all participants as well as Month 9 for those enrolled prior to May 2022. Participants enrolled prior to May 2022 will complete surveys at months 3, 6, 9, and 12, and will use home specimen kit for DBS collection, TFV-DP testing, at months 6 and 12. Participants enrolled after May 2022 will complete surveys at months 3 and 6, and will use home specimen kit for DBS collection, TFV-DP testing at Month 6.

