### **7.1 HIV Testing**

HIV testing will be done for each study visit. All HIV testing will be conducted using a 4th generation Antibody Antigen (AbAg) test. An additional rapid HIV test may be used at the in-person baseline visit prior to determining eligibility to continue with the study. The HIV testing at follow-up visits for the intervention participants will be done using a self-finger prick collection and DBS card. Specimens with a reactive result will undergo confirmatory testing per CDC algorithm (Appendix 4) and participant will be asked to stop taking PrEP. If confirmed, results will be returned to participants by study staff experienced in HIV care linkage.

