### **7.2 STI Testing**

All participants will be tested for Hepatitis B (HBsAg), Hepatitis C (anti-HCV), syphilis (EIA and RPR), and pharyngeal, urethral, and rectal gonorrhea and chlamydia at Baseline. Intervention participants will be tested for syphilis, gonorrhea, and chlamydia (pharyngeal, urethral and rectal) at quarterly follow-up visits.

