### Study Visits and Procedures Schedule

**Study Visits and Procedures**

	Online Screening	Baseline	1 Month	3 Months	6 Months	9 Months	12 Months
Screening consent	X						
Obtain demographic, risk data, and initial eligibility	X						
Study informed consent		X					
Locator information ( including 2 alternative contacts )		X					
HIV rapid test		X					
HIV 4th gen		X					
Creatinine clearance		X					
Syphilis (RPR)		X					
Hepatitis B and C screening		X					
Urine for CT/NG		X					

Oral & Rectal swabs for CT/NG		X		I	I	I	I
Confirm eligibility		X					
Download app		X					
Gilead financial screening		X					
Provide PrEP prescription		X					
Telemedicine visit				I*	I*	I*	I*
Electronic Survey		X	X	X	X	X	X
DBS collection for TFV-DP					X		X
Provide incentive		X	X	X	X	X	X
Provide active referral		C					I

\* as needed

Legend:	
X	All Participants
I	Intervention Only
C	Control Only

### Appendix 3

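### HIV and STI incidence are listed across arms, but follow-up study STI tests cover the intervention arm only; one adjusted model also conditions on eligibility that changes after randomisation

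*Combined protocol and SAP*

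**What the plan says.** **Outcomes.** Section 9.2.1 ends its list of secondary analyses with: "Other specific and aggregate measures of safety include: renal function, HIV incidence, and incident bacterial STI across study arms". It names no formal test and no data source for these outcomes.

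**Follow-up testing by the study.** Section 7.2 tests everyone for STI at baseline, and then: "Intervention participants will be tested for syphilis, gonorrhea, and chlamydia (pharyngeal, urethral and rectal) at quarterly follow-up visits". Section 6.3 agrees: "For intervention participants, home specimen kits for HIV and STI testing will be sent at months 3 and 6" (later enrollees; earlier enrollees also at months 9 and 12). On HIV, section 7.1 says "HIV testing will be done for each study visit", with no arm named, but gives a follow-up method for one arm: "The HIV testing at follow-up visits for the intervention participants will be done using a self-finger prick collection and DBS card".

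**Control arm.** Section 3.1 describes "standard of care control (i.e. patients being seen quarterly in clinic with a provider". Section 5.1 gives controls the parts of the app needed for surveys and for tracking the TFV-DP card.

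**Adjusted models.** Item (1) of section 9.2.1 controls for changes in CDC-defined PrEP eligibility over time, with an eligibility-by-arm interaction. Appendix 3 counts a reported or diagnosed STI in the past 6 months towards eligibility. Section 9.2.1 also treats medication self-efficacy as a potential confounder, without saying when it is measured; section 9.3 lists medication adherence self-efficacy as a possible mediator.

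**The concern.** A laboratory result from a scheduled kit in one arm and an infection that happens to become known in the other are not the same measurement. If the two are set side by side as incidence by arm, part of any difference may be a difference in recording.

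Section 10.2 names behavioral disinhibition as a possible risk of remote care, and section 8.1 has the DSMB monitor disinhibition and HIV seroconversion. A higher recorded STI count under PrEP@Home could be taken as that harm when it partly shows fuller capture. Equally, it could hide a real reduction.

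The second issue is interpretation. Eligibility during follow-up can be changed by the arm itself, and through its STI element it may also be recorded differently by arm. A model that conditions on it does not estimate the effect of assignment. The same holds for self-efficacy if a follow-up value is used: it cannot serve in one model both as a confounder to be removed and as a step on the causal pathway.

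**Working it through.** **The plan's own figure.** None is given for HIV or STI. The only power statement (9.2) concerns TFV-DP: 80% power for a 15.8-point difference from a control proportion of 0.50. With 10% loss (119 and 238), a pooled two-sided z-test and 0.50 versus 0.658, power is 0.82. The point here does not depend on it.

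**Step 1: possible routes for control-clinic follow-up results.**

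| Section | What it provides |
|---|---|
| 4 | Release form; results go from the study to the provider |
| 6.3 | Optional authorization; pharmacy fill dates and quantities |
| 10.1 | Partial HIPAA waiver that may be used at some sites, for results collected for PrEP prescribing; no control follow-up use named |
| 5.1, 6.1.1 | Designated clinics, but a control may use a preferred local provider, so these clinics need not cover every control |
| 6.2, 6.5.1 | Baseline survey covers HIV/STI testing history; the follow-up domains named include no diagnosis item, but the list is open |
| 3.8, 6.4 | HIV-positive participants leave the study, not limited to one arm, so control seroconversions can become known |

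No row describes transfer of control-clinic follow-up results to the study. Self-report remains possible.

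**Step 2: effect on an STI ratio.** Apparent ratio = true ratio × (intervention capture ÷ control capture).

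From the plan: 264 and 132 randomised (5.2) and 10% loss (9.2), so 264 × 0.9 = 237.6 and 132 × 0.9 = 118.8. Six months is used because it is the follow-up that all participants share: "Participants enrolled after May 2022 will complete surveys at months 3 and 6". Assumed: 60 STI per 100 person-years in both arms, and the capture shares.

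- Intervention, full capture: 237.6 × 0.5 × 0.6 = 71.3 events.
- Control, events occurring: 118.8 × 0.5 × 0.6 = 35.6.
- SE of the log ratio = √(1/e_I + 1/e_C), with e the recorded events.

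| Control capture | Recorded events, intervention vs control | Apparent ratio (95% CI) | Ratio if intervention capture is 90% |
|---|---|---|---|
| 100% | 71.3 vs 35.6 | 1.00 | 0.90 |
| 90% | 71.3 vs 32.1 | 1.11 (0.73–1.69) | 1.00 |
| 70% | 71.3 vs 24.9 | 1.43 (0.91–2.25) | 1.29 |
| 50% | 71.3 vs 17.8 | 2.00 (1.19–3.36) | 1.80 |

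Masking works the same way: a true ratio of 0.70 with 70% control capture appears as 0.70 ÷ 0.70 = 1.00. The ratios do not depend on the assumed rate; the intervals do. The intervals treat repeat infections in one man as independent, so they are probably too narrow.

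**Step 3: HIV.** At an assumed 1 per 100 person-years over 6 months: 237.6 × 0.5 × 0.01 = 1.19 and 118.8 × 0.5 × 0.01 = 0.59 expected cases. That is too few for a contrast even with full capture. What matters is that the source of each case is shown.

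**Step 4: adjustment (1).** Eligibility over time is measured after randomisation, one of its criteria is STI, and study STI testing after baseline is in one arm. No bias figure is given: it would depend on how far the arm changes true eligibility, for which the documents have no input.

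**The case against.** The strongest reply is that control participants are tested in routine care and that both arms answer the same surveys. Section 6.2 includes testing history, section 6.5.1 covers what physicians usually assess at quarterly visits, and adjustment (1) tracks eligibility in each arm under a definition that accepts a reported STI. That points towards self-report in both arms. The copy reviewed also lacks the consent pages, some appendix pages and the survey instruments, so a route could exist there. All of this stands, and it limits the claim to what the available text describes.

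It is also true that section 9.2.1 promises no formal test and that section 9.3 analyses seroconverters separately. That lowers the stakes. It does not make a comparison from unequal sources safe to read, given what sections 8.1 and 10.2 ask people to watch for.

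The schedule table in the appendix is broken in the extracted text and shows several follow-up tests for neither arm. It is not relied on; section 7.2 is enough.

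A reader might infer more than the documents support:

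- *Controls go untested.* Sections 3.1 and 5.1 give them quarterly standard care.
- *A false safety signal of known probability.* No test is specified and all capture shares are assumed.
- *STI counts could stop the trial.* Section 8.1 does not name STI among the monitored factors.
- *Baseline CDC eligibility is useless as a covariate because everyone meets it.* Section 3.5.3 also admits sexually active African American MSM without that indication, and section 3.1 requires at least 50% Black participants, that is, at least 198 of 396. It may well vary.

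**Conclusion.** The point holds in two limited parts and should be dealt with.

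**Capture.** For STI, the study's own follow-up laboratory source covers one arm, and the available text describes no matching source for the other. For HIV, the same follows from section 6.3, but section 7.1 can be read differently and the two must be reconciled. The size is unknown. It is nil if capture is equal; the apparent ratio is 1.11 to 2.00 for assumed control capture of 90% down to 50% with full intervention capture, and 1.00 to 1.80 if intervention capture is itself 90%. At 90% and 70% control capture the illustrated six-month intervals include 1.

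**Adjustment.** Adjustment (1), and any model using follow-up self-efficacy, cannot be presented as the adjusted effect of assignment. The bias is not quantified.

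The primary intent-to-treat TFV-DP comparison is not affected, because section 3.1 specifies identical kit collection in both arms. Renal function is outside the point; section 6.3 has creatinine tested at month 3 in all participants. Confidence is medium, mainly because the survey instruments and some pages were not available.

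**What to change.** 1. Reconcile sections 6.3 and 7.1 on which arm has follow-up HIV testing by the study.
2. In section 9.2.1 and the DSMB report template, add wording such as: *Results of study-laboratory tests done in one arm only are descriptive and support no between-arm conclusion. Between-arm comparisons of HIV or STI use only a source collected alike in both arms, such as the same survey item. All known seroconversions and self-reported diagnoses are reported by arm, with their source and the number of participants tested or reporting a test.* If a route for control-clinic results exists, name it there.
3. Label adjustment (1) exploratory and non-causal. It can still describe whether men stop PrEP when no longer indicated. In models presented as adjusted arm effects, use baseline values only: self-efficacy, motivation if collected at baseline, and baseline CDC eligibility if it varies. Keep post-randomisation values for the mediation analysis in section 9.3.

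The cost is wording, a source column and a tested-count per arm, and at most one or two survey items if they are not already asked. No tests or visits are added. The trial gives up a formal laboratory-based STI contrast between arms, and an HIV contrast unless item 1 settles on testing in both arms. Changing eligibility is then studied only as an exploratory question.
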